### **7.8.2. Value Evidence and Outcomes Endpoints (Exploratory)**

- The “Reason for Switch” question will be administered at Day 1 (Baseline) for patients randomized from oral SOC, to assess the reasons for willingness to switch ART.
- The “Reason for Switch” question will be administered at Day 1(Baseline) for patients randomized from CAB LA + RPV LA every 4 weeks in ATLAS, to assess the reasons for willingness to continue long-acting ART.
- A preference questionnaire will be administered to participants receiving oral bridging during the Maintenance and/or Extension Phases in order to explore preference for CAB + RPV LA Q4W or Q8W compared to daily oral HIV medication at W152 or upon WD visit if occurred at or before Week 152.

**7.8.3. Guidance for administering the different versions of HIVTSQc, Preference and Reason for Switch Questionnaires in ATLAS-2M**

*For the questionnaires not included below, HIVTSQs, HAT-QoL, ACCEPT and PIN, there only exists one version of each PRO that will be administered to all patients.*

Questionnaire	Version	Week visit in ATLAS-2M	Treatment Arm in ATLAS-2M	Treatment before entering ATLAS-2M	Patients in Extension phase in ATLAS
HIVTSQc	Q4W ATLAS to Q4W ATLAS-2M	Week 48 / Withdrawal	Currently on Q4W	Randomized at Day 1 in Q4W arm in ATLAS	Even if patients remained in extension phase in ATLAS consider only the initial arm they were randomized in Day 1 in ATLAS
	Q4W ATLAS to Q8W ATLAS-2M	Week 48 / Withdrawal	Currently on Q8W	Randomized at Day 1 in Q4W arm in ATLAS	
	SOC to Q4W or Q8W ATLAS-2M	Week 48 / Withdrawal	Currently on Q4W or Q8W	Any SOC treatment:  Randomized at Day 1 in SOC in ATLAS or coming outside of ATLAS	
Preference	Injection to Injection treatment	Week 48 / Withdrawal	Currently on Q8W	Randomized at Day1 in Q4W arm in ATLAS	Even if patients remained in extension phase in ATLAS consider only the initial arm they were randomized in Day 1 in ATLAS
	Oral to Injection treatment	Week 48 / Withdrawal	Currently on Q4W or Q8W	Any SOC treatment:  Randomized at Day 1 in SOC in ATLAS or coming outside of ATLAS  Continuing	

Questionnaire	Version	Week visit in ATLAS-2M	Treatment Arm in ATLAS-2M	Treatment before entering ATLAS-2M	Patients in Extension phase in ATLAS
				Q4W from ATLAS	
	Reason for Oral Bridging and Preference questionnaire	Week 152 / Withdrawal	Currently on Q4W or Q8W	SOC and Q4W from ATLAS	Not applicable.
Reason for Switch		Day 1	Currently on Q4W or Q8W	Any SOC treatment:  Randomized at Day 1 in SOC in ATLAS or coming outside of ATLAS	Administer again even if patients were administered the “reason for switch” at week 52 in ATLAS.
Reason for Continuation		Day 1	Currently on Q4W or Q8W	Randomized at Day 1 in Q4W arm in ATLAS	

## 8. DATA MANAGEMENT

- For this study participant data will be entered into GSK defined eCRFs, transmitted electronically to GSK or designee and combined with data provided from other sources in a validated data system.
- Management of clinical data will be performed in accordance with applicable GSK standards and data cleaning procedures to ensure the integrity of the data, e.g., removing errors and inconsistencies in the data.
- Adverse events and concomitant medications terms will be coded using Medical Dictionary for Regulatory Activities (MedDRA) and an internal validated medication dictionary, GSKDrug.
- eCRFs (including queries and audit trails) will be retained by GSK, and copies will be sent to the investigator to maintain as the investigator copy. Participant initials will not be collected or transmitted to GSK according to GSK policy.

Please refer to [Appendix 10](#) in Section 11.10 for study management information during the COVID-19 pandemic.

## 9. STATISTICAL CONSIDERATIONS AND DATA ANALYSES

The study is designed to demonstrate that the antiviral effect of Q8W dosing with CAB LA + RPV LA is non-inferior to Q4W dosing CAB LA + RPV LA in subjects stably suppressed on an oral SOC regimen or Q4W CAB LA + RPV LA regimen prior to randomization. Non-inferiority in the proportion of participants with HIV-RNA  $\geq 50$  c/mL at Week 48 (defined by the US FDA snapshot algorithm) can be concluded if the upper bound of a two-sided 95% confidence interval for the difference between the two treatment arms (Q8W – Q4W) is less than 4%.

If  $f_{Q8W}$  is the snapshot failure rate for Q8W CAB LA + RPV LA, and  $f_{Q4W}$  is the snapshot failure rate for Q4W CAB LA + RPV LA then the hypotheses can be written as follows:

$$H_0: f_{Q8W} - f_{Q4W} \geq 4\% \quad \text{vs} \quad H_1: f_{Q8W} - f_{Q4W} < 4\%$$

### 9.1. Sample Size Considerations

This study will randomize approximately 510 participants per arm. Assuming the true proportion with HIV-1 RNA  $\geq 50$  c/mL is 3% for the Q8W arm and 2% for the Q4W arm, a non-inferiority margin of 4%, and a 2.5% one-sided significance level, this sample size would provide at least 85% power to show non-inferiority at Week 48 (using unpooled Z test statistic). With this sample size, 90% power would be achieved assuming a 1% treatment difference and true proportions with HIV-1 RNA  $\geq 50$  c/mL of 2.63% for the Q8W arm and 1.63% for the Q4W arm.

With 510 subjects per arm and assuming an observed proportion HIV-RNA  $\geq 50$  c/mL is 2% for Q4W, the largest observed treatment difference to achieve non-inferiority with respect to a 4% margin is 1.92 percentage points. This equates approximately to observing an excess of 10 subjects on the Q8W arm (10 subjects on Q4W vs. 20 subjects on Q8W).

This sample size of 510 participants per arm will also provide at least 90% power (using unpooled Z test statistic) to show non-inferiority in the proportion of participants with plasma HIV-1 RNA  $< 50$  c/mL (per FDA's snapshot algorithm) at Week 48 over a range of true response rates, on the basis of a -10% non-inferiority margin and 2.5% one-sided significance level (see [Figure 15](#)). For example, assuming true response rate for the Q8W arm and Q4W arm are both 92%, the power is  $\geq 99\%$  to show non-inferiority for this key secondary endpoint.

#### 9.1.1. Rationale for non-inferiority margin

A non-inferiority margin of 4% has been chosen for this study because a snapshot proportion with HIV-1 RNA  $\geq 50$  c/mL at Week 48 in this range is considered clinically tolerable given the Q8W regimen will offer important advantages over the Q4W regimen

such as reduced injection frequency, and may offer better adherence and treatment satisfaction. This margin is also in concordance with the current FDA Guidance for Industry (FDA, 2015), which is the most current regulatory guidance from either the European Medicines Agency (EMA) or FDA and includes specific recommendations regarding switch studies.

### 9.1.2. Assumption for Snapshot Proportion with HIV-RNA $\geq 50$ c/mL at Week 48 (Primary Endpoint)

For the sample size calculation, assumptions regarding the true proportion with HIV RNA  $\geq 50$  c/mL for each arm were informed by data from the LATTE-2 Phase 2b study (Table 11). These data suggest a rate of 2% for Q4W and a possibly higher rate in the neighbourhood of 3% for Q8W.

Two important changes to the current study in relation to the LATTE-2 study were also considered in setting the sample size. Firstly, the loading dose schedule for Q8W has been modified in an attempt to optimize the pharmacokinetics of CAB LA + RPV LA. Secondly, a re-testing strategy (see Section 5.5.5.1) has been added to reduce the number of subjects counted as having HIV RNA  $\geq 50$  c/mL in the primary analysis at key timepoints because of transient blips (consistent with the FDA's guidance for the Snapshot endpoint). Through these changes, it is possible that the proportions with HIV RNA  $\geq 50$  copies/mL will be lower than that observed in the LATTE-2 study.

**Table 11 Snapshot Analysis Outcomes for LATTE-2 Phase IIb Study of CAB LA + RPV LA (Intent-to-Treat Maintenance Exposed Population)**

Week 48			
Study	Maintenance Treatment Arm	HIV-RNA <50	HIV-RNA $\geq 50$
LATTE-2 (ITT-ME) a	CAB LA + RPV LA Q8W (N=115)	92%	8/115 (7%)
	CAB LA + RPV LA Q4W (N=115)	91%	1/115 (<1%)
	Pooled LA (N=230)	92%	6/230 (4%)
	Oral CAB + 2NRTIs (N=56)	89%	1/56 (2%)
Week 96			
LATTE-2 (ITT-ME) b	CAB LA + RPV LA Q8W (N=115)	94%	5/115 (4%)
	CAB LA + RPV LA Q4W (N=115)	87%	0/115 (0%)
	Pooled LA (N=230)	90%	5/230 (2%)
	Oral CAB + 2NRTIs (N=56)	84%	5/56 (2%)

a) Participants had HIV-1 RNA <50 c/mL at Week -4 and received oral CAB 30 mg + 2 NRTIs as initial induction period therapy from Week -20 to Day 1.

b) Participants had HIV-1 RNA <50 c/mL at Week 20 and switched from oral CAB 30 mg + 2 NRTIs to Oral CAB 30 mg + RPV at Week 24.

### 9.1.3. Assumption for Response Rate at Week 48 (Secondary Endpoint)

Given the response rates shown in Table 11, a reasonable assumption for the true response rate (HIV-1 RNA <50 c/mL) for both arms is 92%.

### 9.1.4. Sample Size Sensitivity

Figure 15a (left panel) shows the sensitivity of the power curve for the primary comparison to different assumed 'true' proportions with HIV-RNA  $\geq 50$  c/mL with 510

randomized participants per arm based on calculations using an unpooled Z test statistic and asymptotic approximation. For example, if the true rate for Q8W is 1.5 percentage points higher than Q4W (green line), then the study would still have over 80% power to meet its primary objective if the Q4W rate is less than 1.3%.

Figure 15b (right panel) shows the impact on power to changes in the sample size assuming a 2% true-rate for Q4W. Power remains at least 80% for sample sizes as low as 425 per arm if the true Q8W rate is at most 1-percentage point inferior to Q4W.

**Figure 15 Sensitivity of Estimated Power for Snapshot Proportion with HIV-RNA  $\geq$  50 c/mL**

[figure not shown]
[figure not shown]

Figure 16a (left panel) shows the sensitivity of the estimated power for the secondary endpoint comparison of response rates (HIV-1 RNA <50 c/mL at Week 48) to different assumed ‘true’ response rates based on calculations using an unpooled Z test statistic and asymptotic approximation. For example, if the true Q8W rate is two percentage points inferior to Q4W (blue line), then power is at least 90% for Q4W rates greater than 82%.

Figure 16b (right panel) shows the impact on power to changes in the sample size assuming an 92% response rate for Q4W. For example, if the true Q8W rate is 3-percentage points inferior to Q4W (green line), then power remains at least 90% for sample sizes as low as 368 per arm.

**Figure 16 Sensitivity of Estimated Power for Snapshot Proportion with HIV-RNA <50 c/mL**

**9.1.5. Sample Size Re-estimation or Adjustment**

No sample-size re-estimation based on response data is planned for this study.

**9.2. Data Analysis Considerations**

**9.2.1. Analysis Populations**

**9.2.1.1. Intent-to-Treat Exposed (ITT-E)**

The ITT-E population will consist of all randomly assigned participants who receive at least one dose of study drug. Participants will be assessed according to their randomized treatment, regardless of the treatment they received. The population used in the primary efficacy analysis will be the ITT-E population.

**9.2.1.2. Per-Protocol Population (PP)**

The Per-Protocol (PP) Population will consist of all participants in the ITT-E Population with the exception of major protocol violators. The PP will be used for sensitivity analysis of the primary endpoint.

**9.2.1.3. PK Population**

The PK Population will include all participants who receive CAB and / or RPV and undergo PK sampling during the study, and provide evaluable CAB and /or

RPV plasma concentration data. Participants in this population will be included in the PK analysis.

#### **9.2.1.4. Safety Population**

The Safety Population will consist of all randomly assigned participants who receive at least one dose of study drug. Participants will be assessed according to actual treatment received. Unless otherwise stated, the Safety Population will be used for safety analyses.

### **9.2.2. Treatment Comparisons**

#### **9.2.2.1. Primary Comparison of Interest**

The primary analysis will be based on the ITT-E population. The primary comparison will be made at a one-sided 2.5% level of significance. Treatment with Q8W will be declared non-inferior to Q4W if the upper end of a two-sided 95% confidence interval for the difference between the two groups (Q8W – Q4W) in the proportion of participants with HIV-RNA  $\geq 50$  c/mL at Week 48 (defined by the US FDA snapshot algorithm) lies below 4%.

#### **9.2.2.2. Other Comparisons of Interest**

- The analysis described above will also be performed using the PP population and the results will be compared for consistency with the results from the ITT-E population. If the primary comparison on interest using the ITT-E population demonstrates non-inferiority of Q8W compared to Q4W then the following key secondary comparisons will be tested: Treatment with Q8W will be declared non-inferior to Q4W with respect to the proportion of participants with HIV-1 RNA < 50 copies/mL at Week 48 (defined by the US FDA snapshot algorithm) if the lower end of a two-sided 95% confidence interval for the difference between in rates (Q8W – Q4W) lies above -10% using the ITT-E population
- Superiority of Q8W compared to Q4W with respect to change from baseline HIVTSQs total score at Week 48 using the ITT-E population and a two-sided 5% level of significance

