#### **9.3.7. Health Outcomes Analyses**

Details of the analyses to be performed for the endpoints described in Section 7.8 will be specified in the reporting and analysis plan. Participant preference for CAB LA + RPV LA every 8 weeks or CAB LA + RPV LA every 4 weeks compared to oral ARV regimen, and preference for CAB LA + RPV LA every 4 weeks compared to CAB LA + RPV LA every 8 weeks will be a key secondary treatment analysis based on the ITT-E population. As another key secondary treatment comparison, superiority of Q8W compared to Q4W

with respect to change from baseline in HIVTSQs total score at Week 48 will be tested at a two-sided 5% significance level using a linear model based on the ITT-E population.

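### Behind the primary gate, <50 c/mL non-inferiority and HIVTSQs superiority are each tested at full level with no order or split, and section 9.3.7 calls preference key although 9.2.2.2 does not list it

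*Protocol*

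**What the plan says.** - **Primary (9.2.2.1).** "The primary comparison will be made at a one-sided 2.5% level of significance". The margin is 4 percentage points on the proportion with HIV-1 RNA ≥50 c/mL at Week 48, in the ITT-E population.
- **Gate (9.2.2.2).** If the ITT-E primary "demonstrates non-inferiority of Q8W compared to Q4W then the following key secondary comparisons will be tested".
- **First key secondary (9.2.2.2).** Non-inferiority on HIV-1 RNA <50 c/mL at Week 48 is declared "if the lower end of a two-sided 95% confidence interval for the difference between in rates (Q8W – Q4W) lies above -10" per cent, which is a one-sided 2.5% test.
- **Second key secondary (9.2.2.2).** This is superiority of Q8W on the HIVTSQs total score, as change from baseline to Week 48. The test is set at full level, "using the ITT-E population and a two-sided 5% level of significance". Section 9.3.7 repeats that this comparison "will be tested at a two-sided 5% significance level using a linear model based on the ITT-E population". It mentions neither the gate nor the <50 c/mL result.
- **Preference (9.3.7).** Participant preference between regimens "will be a key secondary treatment analysis based on the ITT-E population". No hypothesis, test or level follows. Section 9.2.2.2 does not list preference, and 7.8.1 lists it as an ordinary secondary endpoint.
- **Multiplicity.** The only statements in the part shown are in 9.2.3.1 (Week 24 analysis) and 9.2.3.2 (IDMC analyses). Both concern the primary Week 48 comparison alone.

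**The concern.** A gate in front of a group of tests protects the test that forms the gate. It does not limit error among the tests behind it when each keeps its full level. Two consequences follow from the rule as written.

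First, the chance of at least one false key secondary claim in favour of Q8W is larger than the one-sided 2.5% used for each test.

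Second, HIVTSQs superiority does not depend on the <50 c/mL result. The primary can succeed while <50 c/mL fails, because the two endpoints treat missing data differently: 9.3.2.1 counts every participant without evaluable data as a non-responder, whereas 9.3.1 counts only some of them as ≥50 c/mL. Table 11 shows how wide that gap can be. The LATTE-2 Q4W arm at Week 48 had 1 of 115 at ≥50 c/mL but only 91% at <50 c/mL, which leaves about 8% in neither group. A satisfaction claim for Q8W could then stand beside a failed efficacy comparison.

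Separately, 9.2.2.2 and 9.3.7 disagree on which analyses are key, so a reader cannot tell how many claims belong to the family.

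**Working it through.** **Inputs.** 510 per arm; primary rates 3% (Q8W) and 2% (Q4W), margin 4%; response 92% in both arms, margin −10%; one-sided 2.5% (all from 9.1). HIVTSQs at two-sided 5% is one-sided 2.5% in the direction favouring Q8W (9.2.2.2).

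**1. Reproduce the plan's own power figures** (unpooled Z).

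Power = Φ[(margin − true disadvantage of Q8W)/SE − 1.96], with SE = √[p₁(1−p₁)/n + p₂(1−p₂)/n].

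- Primary: SE = √[(0.0291 + 0.0196)/510] = 0.00977. Power = Φ(0.03/0.00977 − 1.96) = Φ(1.11) = 86.7%. The plan says at least 85%.
- <50 c/mL at 92%/92%: SE = √(2 × 0.0736/510) = 0.01699. Power = Φ(0.10/0.01699 − 1.96) = Φ(3.93) = 99.996%. The plan says at least 99%.

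Both agree with the plan. It states no family-wise error figure for the key secondaries.

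**2. Error behind the open gate, both secondary nulls true, claims in favour of Q8W.**

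- Independent tests: 1 − 0.975² = 4.94%.
- Upper bound without independence: 2 × 2.5% = 5.0%.
- Positively correlated tests (bivariate normal, 0.05 minus the probability that both reject): 4.5% at correlation 0.5 and 3.9% at 0.8.
- If the gate itself opens with probability 86.7%, independently of the secondaries: 0.867 × 4.94% = 4.3%.

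The reference value is 2.5%. The correlations are assumptions; the part of the protocol shown gives none.

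**3. Error if only one secondary null is true.** It is the nominal level of that test, so there is no inflation.

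**4. Error under a fixed sequence** (primary, <50 c/mL, HIVTSQs, each only if the previous step is met). Any false claim requires false rejection of the first true null in the order, which has probability at most 2.5% one-sided. The family is held at 2.5% whatever the correlation.

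**5. What the sequence costs HIVTSQs.** It loses its test only when the <50 c/mL step fails.

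- At 92%/92% that step passes with probability 99.996%.
- If Q8W is truly 90%: SE = √[(0.0736 + 0.0900)/510] = 0.01791 and power = Φ(0.08/0.01791 − 1.96) = 99.4%.

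**The case against.** **Order is a matter for the RAP.** Sections 9.2.3, 9.3.2.2 and 9.3.7 send analysis details there, it is not shown, and it may fix a sequence. This stands in part: the RAP may already have closed the gap. But 9.2.2.2 does not defer on this point. It states the gate, the decision rules and the levels, and 9.3.7 fixes the HIVTSQs level again. Followed as written, those rules allow full-level testing of both endpoints.

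**The listing may imply an order.** The <50 c/mL comparison comes first, and the bullet structure may have suffered in the reading of the PDF. Being listed first is not a condition, however, and no wording makes HIVTSQs depend on <50 c/mL.

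**4.9% is a worst case.** This stands. The <50 c/mL null means that Q8W is at least 10 points worse. With 92% response on Q4W, Q8W would have to be at 82% or lower. At the planned ≥50 c/mL rates, that leaves about 100 − 82 − 3 = 15% without virologic data on Q8W against 100 − 92 − 2 = 6% on Q4W. That is far from the planning case, where a sequence would hardly ever change the HIVTSQs conclusion.

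**The protocol may be too late to change.** Section 11.13.8.2 cites observed Week 96 concentrations and Maintenance-phase adverse event rates, so the Week 48 tests have probably been run. A sequence written now might not count as prespecified. This stands and limits the fix.

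**Stronger readings that a reader might infer.**

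- That error is uncontrolled across all claims. It is not: the gate holds the primary at one-sided 2.5%.
- That three key claims give 1 − 0.975³ = 7.3%. This assumes a full-level preference test that 9.3.7 never specifies. In the 7.8.3 table, the injection-to-injection version goes only to participants now on Q8W, so that version has no Q4W comparator arm.
- That HIVTSQs is the trial's only superiority claim. The first part of the protocol is not shown, so this cannot be confirmed.

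**Conclusion.** The point holds within the key secondary family only. The primary conclusion is unaffected.

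As written, two key secondary tests share one gate and each uses its full level. One-sided error for claims favouring Q8W can then reach about 4.9% against 2.5% if both nulls are true and the tests independent, falling to 4.5% or 3.9% at correlations of 0.5 or 0.8. The practical weakness is that HIVTSQs superiority may be claimed after <50 c/mL non-inferiority has failed.

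The preference item in 9.3.7 is an inconsistent label. It adds no error unless a formal claim is drawn from it, and the protocol sets up no such claim.

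The conclusion rests on the text shown; an order prespecified in the RAP would resolve the error question but not the mismatch between 9.2.2.2 and 9.3.7.

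**What to change.** - **9.2.2.2:** state the sequence as (1) primary non-inferiority; (2) non-inferiority on <50 c/mL at −10%; (3) HIVTSQs superiority at two-sided 5%. Each step is tested only if the one before it is met.
- **9.3.7:** label preference a descriptive secondary analysis, and refer to 9.2.2.2 for the conditions on the HIVTSQs test.
- **If Week 48 has already been analysed:** cite the order prespecified in the RAP, if there is one. If there is none, report the HIVTSQs result as not multiplicity-controlled and do not present a newly written sequence as prespecified. Section 9.3.1 already allows changes to the plan to be described in the RAP or the study report.

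The cost is a few sentences. The real downside is that HIVTSQs superiority cannot be claimed if the <50 c/mL step fails, a negligible loss of power under the planning assumptions.

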### **9.2.3. Planned Analyses**

At least 4 analyses will be conducted to evaluate the objectives of the protocol after all subjects have completed their visits at Week 24, Week 48, Week 96, and Week 152 respectively. Further data cuts and analyses may be conducted as necessary in order to support regulatory submissions and publications (first publication at Week 48). The Week 48 analysis will be primary and no results will be shared publicly until Week 48 analysis is complete. Full details for the primary Week 48 analysis (and preliminary Week 24 analysis) will be prespecified in the RAP prior to the database freeze for the Week 24 analysis and sponsor review of any summary of data grouped by actual treatment arm.

### **9.2.3.1. Week 24 data analyses**

An analysis of data through Week 24 will be conducted when all subjects have completed their Week 24 visit, with the intent of expediting submission of results to health authorities.

The analyses described in Section 9.3.2.2, Section 9.3.3 and Section 9.3.6 will be performed. Health outcomes analyses will not be performed.

There is no intention to stop the study early if positive efficacy findings are seen at Week 24 and a formal hypothesis test of non-inferiority at Week 24 will not be evaluated. The analysis at Week 48 is primary and will overrule the findings based on the Week 24 data. Therefore, no multiplicity adjustment to the primary Week 48 treatment comparisons is needed because of the analysis of Week 24 data.

Neither investigators nor subjects will be informed of the results of the Week 24 data analysis. Sponsor staff will only review aggregate data by actual treatment arm after the Week 24 IDMC evaluation is complete as required in the preparation of submission documents.

